STUDY PROTOCOL

Exploring Predictors of Quality of Life in Older Adults with End-Stage Kidney Disease Receiving In-Center Hemodialysis: A Cross-Sectional Analysis of Sociodemographic, Dialysis-specific, Biopsychosocial, and Activity-Related Factors

Overview

The global prevalence of end-stage kidney disease (ESKD) is increasing, particularly among older adults. Maintenance in-center hemodialysis (ICHD), while life-sustaining, imposes significant treatment and symptom burdens that disproportionately affect older patients with coexisting frailty, multimorbidity, and psychosocial challenges.

While older adults with ESKD consistently prioritize quality of life (QoL) over survival, this outcome remains underrepresented in clinical research. Health-Related Quality of Life (HRQoL) measures are often used as proxies but may not fully capture what matters most to patients, especially during major transitions like dialysis initiation. Differences in HRQoL instruments also create variability in evaluations and cost-effectiveness estimates.

This study seeks to address these gaps by examining overall QoL using an individualized, validated instrument, and identifying its key determinants among older ICHD patients.

Study objectives

Primary Objective:

To identify key factors associated with overall QoL, as measured by the Amnestic Comparative Self-Assessment (ACSA) and a range of sociodemographic, dialysis-specific, biopsychosocial, and activity-related factors, in older adults receiving ICHD.

Secondary Objectives:

To examine the relationship between overall QoL (ACSA) and HRQoL instruments (EQ-5D-3L, EORTC QLQ-C30, QLQ-MY20).

To explore clusters of patients with similar QoL profiles using multivariate and cluster analysis.

Study design

Type: Observational

Model: Cross-Sectional

Time Perspective: Prospective

Reporting Guidelines: STROBE

Study population

Inclusion Criteria

Adults aged ≥65 years

Receiving maintenance in-center hemodialysis (ICHD)

Able to provide informed consent

Sufficient cognitive and language ability to complete questionnaires in Dutch

Exclusion Criteria

Undergoing ICHD due to an acute hospital admission

Formal diagnosis of severe psychiatric or cognitive disorders (e.g., dementia)

Inability to understand or respond adequately to study assessments

Study setting and recruitment

Participants are recruited from four hospitals in Flanders, Belgium. Hospitals are selected to represent a mix of urban, rural, academic, and regional settings. Recruitment and data collection occurs during one to three consecutive dialysis sessions, depending on the participant's condition.

Study procedures and data collection

Assessments are administered face-to-face by an independent researcher unaffiliated with the dialysis units. The assessment session lasts approximately 45 minutes and includes validated instruments across several domains.

Ethical considerations

This study was approved by the Ethical Committee of Ghent University Hospital (B670201837264) and is conducted in accordance with the Declaration of Helsinki. All participants receive detailed information about the study and provide written and verbal informed consent prior to participation.

Outcome measures

Primary outcome/measure

Measure: Overall Quality of Life (QoL)

Instrument: Amnestic Comparative Self-Assessment (ACSA)

Description: Participants self-rate their current QoL on a scale from -5 (worst time in life) to +5 (best time), anchored to their own past experiences.

Secondary outcomes/measures

Measure: Dialysis and sociodemographic characteristics

Instrument: Medical records

Description: Age, marital status, living situation, (grand)children, dialysis vintage, hospital admissions

Measure: Comprehensive Geriatric Assessment

Instrument: Multi-domain assessment

Description: Includes (risk of) falls using St. Thomas's Risk Assessment Tool in Falling Elderly

Inpatients (STRATIFY), risk of dementia using Mini-Cog, nutritional risk using the NRS-2002, pain using a VAS-scale, questions about vision, hearing, and continence

Measure: Frailty

Instrument: Groningen Frailty Indicator (GFI)

Description: A multidimensional frailty measure including biopsychosocial factors

Measure: Activity

Instrument: Brussels Integrated Activity Scale (BIA)

Description: Measures basic-, instrumental-, and advanced activities of daily living

Measure: Health-Related Quality of Life

Instruments: EuroQol 5-Dimension 3-Level questionnaire (EQ-5D-3L), the EORTC QLQ-C30, the EORTC QLQ-MY20

Description: the EORTC QLQ-C30 is a multidomain HRQoL instrument validated in chronic illness populations focusing on symptom and functioning scales, the EORTC QLQ-MY20 is often used as a supplemental module, focusing on disease burden, side effects, future perspective, body image

STATISTICAL ANALYSIS PLAN

General

Statistical analysis consists of four stages: descriptive analysis, univariate analyses, multivariate analyses, and cluster analysis. Two-tailed tests are used, with $p < 0.05$ considered statistically significant unless otherwise specified. Data distributions to be assessed for normality using the Shapiro-Wilk test. Missing data are handled using listwise deletion per questionnaire, with the assumption that missingness was random. All statistical analyses are performed using IBM SPSS Statistics version 29.0.2.0.

Stage 1: Descriptive analysis

Descriptive statistics are calculated for all demographic, clinical, functional, psychosocial, and quality of life variables. This includes:

- Overall QoL (ACSA)
- Participant demographics (age, sex, dialysis vintage, hospital setting)
- Comprehensive Geriatric Assessment (STRATIFY, Mini-Cog, GDS-4, NRS-2002, Pain VAS-scale, Questioning on vision, hearing, continence)
- Frailty score (GFI)
- ADL functioning (BIA; basic, instrumental, advanced activities of daily living)
- HRQoL scores (EQ-5D-3L, EORTC QLQ-C30, QLQ-MY20)

Stage 2: Univariate analyses

Univariate analyses are conducted to identify associations between the independent variable (ACSA) and the dependent variables (secondary outcomes).

Analyses are stratified based on variable type: Dichotomous variables: Mann-Whitney U test; Categorical variables with ≥ 3 groups: Kruskal-Wallis test; Ordinal and continuous variables: Spearman's rank correlation coefficients

Variables with a p -value < 0.05 in univariate testing are considered for multivariable modeling.

Additional exploratory analyses examine the relationship between the ACSA score and HRQoL instruments/domains, including the EQ-5D utility index.

Stage 3: Multivariate Analysis

A stepwise multiple linear regression analysis is performed to identify independent predictors of overall QoL (ACSA score). Variables significantly associated with the ACSA in univariate analysis are entered sequentially using forward selection. Multicollinearity is assessed, and variables with high collinearity were excluded.

The model is evaluated using Adjusted R² to assess the proportion of explained variance. Regression coefficients (unstandardized B), standardized beta weights, t-values, and significance levels are reported for each step.

Stage 4: Cluster Analysis

To explore subgroups of participants with distinct QoL profiles, a two-step cluster analysis is performed:

-Hierarchical clustering using Ward's method to determine the optimal number of clusters based on the dendrogram.

-K-means clustering to define group composition using the dependent variable (ACSA) and significant independent variables identified in prior analyses.

Sensitivity Analyses

The robustness of regression findings is checked using alternative model orders and bootstrapping methods. Variance inflation factors (VIF) are used to monitor multicollinearity.

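### Deleting missing data by questionnaire rather than by scale can discard fully answered scales of the multi-scale instruments and cost avoidable precision

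*Combined protocol and SAP*

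**What the plan says.** The only missing-data rule is in the SAP, General: "Missing data are handled using listwise deletion per questionnaire", on the stated assumption that values are missing at random. It does not say whether a blank item, a missing scale score or an uncompleted form triggers deletion. No rule is given for scoring a partly answered scale.

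The unit of analysis is described elsewhere:

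- Protocol, Outcome measures: the QLQ-C30 is a "multidomain HRQoL instrument validated in chronic illness populations focusing on symptom and functioning scales", and the QLQ-MY20 is a supplemental module "focusing on disease burden, side effects, future perspective, body image".
- SAP, Stage 2: "Additional exploratory analyses examine the relationship between the ACSA score and HRQoL instruments/domains, including the EQ-5D utility index".
- SAP, Stage 1: the BIA is listed at basic, instrumental and advanced levels, while the GFI is listed as one frailty score.

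The SAP's Sensitivity Analyses cover model order, bootstrapping and variance inflation factors. None concerns missing data.

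**The concern.** Listwise deletion normally drops a case when any value in the defined set is missing. Here the set is the questionnaire, but what is correlated with the ACSA is a scale or domain. A patient with one blank on the QLQ-C30 would then lose all its functioning and symptom scales, although most were answered completely. The same holds for the QLQ-MY20 and for the three BIA levels.

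Two parts of the plan are exposed. One is the secondary objective relating the ACSA to the HRQoL instruments. The other is Stage 2 screening, where p < 0.05 decides which variables are considered for the regression. A smaller n there widens intervals and also changes which variables qualify. Through the BIA this reaches the activity-related factors named in the primary objective.

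This point is about the unit of deletion. It does not depend on whether the missing-at-random assumption is right.

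**Working it through.** **No figure to reproduce.** The documents give no sample size, effect size, expected missing rate or number of items per scale. What follows is an illustration.

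**Assumed inputs, not in the documents.** k = 30 or 20 items per form (suggested only by the instrument names); s = 5 items per scale; items blank independently with probability m, from 0.1% to 2%.

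**Formulas.** Share of patients kept under per-questionnaire deletion = (1 − m)^k. Share kept under per-scale deletion = (1 − m)^s. Interval width varies roughly as 1/√n, so the width ratio is √[(1 − m)^s / (1 − m)^k]. This isolates the deletion unit; nothing is prorated.

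| m | Kept per 5-item scale | Kept per 30-item form | CI wider, 30 items | CI wider, 20 items |
|---|---|---|---|---|
| 0.1% | 99.5% | 97.0% | 1.3% | 0.8% |
| 0.5% | 97.5% | 86.0% | 6.5% | 3.8% |
| 1% | 95.1% | 74.0% | 13.4% | 7.8% |
| 2% | 90.4% | 54.5% | 28.7% | 16.4% |

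Example at m = 1%: 0.99^5 = 0.951, 0.99^30 = 0.740, and √(0.951/0.740) = 1.134.

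**Power.** Further assume N = 100 and a true correlation of 0.30, with the SAP's two-sided 0.05. By the Fisher z approximation, power = Φ[atanh(0.30)·√(n − 3) − 1.96], where n is 100 times the share kept:

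- m = 0.5%: 85.3% per scale (n = 97.5) against 80.5% per questionnaire (n = 86.0).
- m = 1%: 84.4% (n = 95.1) against 74.1% (n = 74.0).
- m = 2%: 82.5% (n = 90.4) against 60.3% (n = 54.5).

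**Adding a half-answered scoring rule.** A scale is then lost only if fewer than half its items are answered. At m = 2%:

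- two items: 0.02² = 0.04%;
- three items: 3 × 0.02² × 0.98 + 0.02³ = 0.12%;
- five items: about 0.01%.

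A single-item scale is still lost at the item rate, 2%. Against this rule, per-questionnaire deletion of a 30-item form gives intervals wider by 7.8%, 16.3% and 35.4% at m = 0.5%, 1% and 2%. The part beyond the table comes from proration, not from the deletion unit.

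**Other missingness patterns.** If a form is either complete or wholly blank, both rules keep the same patients and the difference is zero. Blanks clustered within patients fall between the two cases.

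**The case against.** **The wording is open.** The sentence can be read to mean that a patient leaves only the analyses of a questionnaire they did not complete and stays in the rest. No answered scale need then be lost. This stands: a reader might infer that one blank certainly discards every scale, and the text does not establish that trigger. But on this reading the SAP has no rule for a partly completed form, and two analysts could reach different n per scale. The same sentence is needed either way.

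**The loss may be small.** Interviews are face-to-face with an independent researcher and can spread over one to three dialysis sessions, which may keep isolated blanks rare. This also stands. A reader might take the 2% row as the expected loss; nothing in the documents supports choosing that row. On the other side, participants are 65 or older and the assessment takes about 45 minutes, so partial forms are plausible.

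**Frailty is not affected in this way.** A reader might extend the point to the GFI. It is listed as a single score, so deletion per questionnaire and per scale coincide. Prorating might recover some GFI totals, but that is a separate argument about partial scoring.

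**Comparability is not restored.** Scale-level handling also gives a different n for each scale, so correlations still rest on different patient sets. They are larger sets, but not a common one. The case for the change is precision.

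**Reach is limited.** The ACSA is a single self-rating, patients stay in the analyses of other instruments, and Stage 2 labels the ACSA–HRQoL analyses exploratory. That limits the consequence. The protocol nevertheless makes this relationship a secondary objective, and Stage 2 screening feeds the primary analysis.

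**Conclusion.** The point holds for the QLQ-C30, QLQ-MY20 and BIA, as an avoidable loss of precision under the ordinary meaning of the rule. It is not shown that the trigger is a single blank item, that the primary outcome or the GFI loses other scales, or that any particular share of patients will be lost.

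For a 30-item form with 5-item scales and independent blanks, the cost runs from intervals about 1% wider at 0.1% item missingness to about 29% wider at 2%. It shrinks with clustering and vanishes if only whole forms are missing. No figure can be given for the BIA, whose item count does not appear. The change is still worth making, because it costs almost nothing and does no harm if few items turn out to be missing.

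**What to change.** Replace the deletion rule in the SAP, General, with:

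> Missing items are handled per scale. Each scale is scored by its instrument's own missing-item rule or, where it has none, from the answered items if at least half are answered. Otherwise only that scale is set to missing, and all other scales of the questionnaire are kept.

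Report n for every scale. Repeat the affected analyses with complete questionnaires only, as a check, and add this to the Sensitivity Analyses.

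The cost is one SAP sentence and a few lines of scoring syntax, with no new data. The downside is that proration assumes the answered items represent the missing ones in the same scale; the complete-questionnaire repeat shows whether the results depend on it.

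### Stage 2 takes its candidate predictors from the secondary outcomes, so HRQoL scales are eligible for the primary regression although the primary objective does not name them

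*Combined protocol and SAP*

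**What the plan says.** - **Screen (SAP, Stage 2).** "Univariate analyses are conducted to identify associations between the independent variable (ACSA) and the dependent variables (secondary outcomes"). Variables reaching p < 0.05 go forward for consideration in the multivariable model.
- **Secondary outcomes (protocol, Outcome measures).** Besides the geriatric assessment, frailty and activity, the list has an HRQoL entry: "EuroQol 5-Dimension 3-Level questionnaire (EQ-5D-3L), the EORTC QLQ-C30, the EORTC QLQ-MY20". The sociodemographic and dialysis entry reads "Age, marital status, living situation, (grand)children, dialysis vintage, hospital admissions".
- **Entry (SAP, Stage 3).** Variables significant in Stage 2 enter by forward selection. Highly collinear variables are dropped, but no cut-off is given and nothing says which of two collinear variables goes.
- **Objectives (protocol).** The primary objective concerns ACSA and "a range of sociodemographic, dialysis-specific, biopsychosocial, and activity-related factors, in older adults receiving ICHD". The title names the same four domains. HRQoL has its own secondary objective: "To examine the relationship between overall QoL (ACSA) and HRQoL instruments (EQ-5D-3L, EORTC QLQ-C30, QLQ-MY20").
- **HRQoL in Stage 2.** After the p < 0.05 rule, a further sentence announces exploratory analyses of ACSA against the HRQoL instruments and domains.
- **Stage 1 list.** It names sex, hospital setting and GDS-4. The protocol's secondary-outcome list names none of the three.
- **Stage 4.** K-means uses ACSA plus the variables found significant in the preceding stages.

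**The concern.** The term secondary outcomes is the SAP's only definition of the candidate pool, and it does not match the primary objective. It takes in three HRQoL instruments that the objective does not name. The protocol's Overview says HRQoL measures often stand in for QoL and may miss what matters most to patients. A model that explains overall QoL by such a proxy answers a different question from which patient factors are associated with it.

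Forward selection makes this matter. A scale that overlaps with frailty, pain or activity, and tracks ACSA more closely than they do, enters first and can leave them too little unexplained variance to enter. They would then be reported as not independently associated with QoL because of what they were made to compete with. Stage 4 inherits the same selection. Two competent analysts could also fit different primary models from this text, and the choice could be made after the results are seen.

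The same sentence leaves the status of sex, hospital setting and GDS-4 unclear. For hospital setting this sits oddly with the recruitment plan: "Hospitals are selected to represent a mix of urban, rural, academic, and regional settings".

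**Working it through.** **1. Candidate pool by reading the lists.** The plan states no candidate count, sample size or correlation, so there is no figure to reproduce.

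- Protocol list without HRQoL: 6 sociodemographic/dialysis items + 7 geriatric assessment items (STRATIFY, Mini-Cog, NRS-2002, pain, vision, hearing, continence) + GFI + 3 BIA levels = 17.
- Literal Stage 2 pool, each HRQoL instrument counted once: 17 + 3 = 20. It is larger if subscales are screened separately.
- Four-domain pool with sex, hospital setting and GDS-4: 17 + 3 = 20.

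The last two pools are equal in number but differ in three members each way.

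**2. Why displacement depends on relative strength.** Let a be the factor–ACSA correlation, h the HRQoL–ACSA correlation and o the factor–HRQoL correlation. Once HRQoL is in the model, the factor's partial correlation with ACSA is

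(a − h·o) / √[(1 − h²)(1 − o²)].

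All values here are assumed. With a = 0.35 and o = 0.50:

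- h = 0.50: (0.35 − 0.25)/√(0.75 × 0.75) = 0.13
- h = 0.35: (0.35 − 0.175)/√(0.8775 × 0.75) = 0.22
- h = 0.25: (0.35 − 0.125)/√(0.9375 × 0.75) = 0.27

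At n = 100 with two predictors (97 degrees of freedom), two-sided p < 0.05 needs a partial correlation of about 1.985/√(1.985² + 97) = 0.20. The first value falls short, the second is marginal and the third passes.

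**3. Simulation of the plan's steps.** Assumptions: multivariate normal data; ACSA rounded to its 11 points with SD about 2; Spearman screen at p < 0.05; forward selection with entry at p < 0.05 (the SAP gives no entry level); no collinearity exclusion; 1,500 replicates per cell. There are three target factors (0.35 with ACSA, 0.40 with each other) and one HRQoL scale (0.50 with each factor). The table gives the mean number of the three factors kept, HRQoL barred vs eligible:

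| HRQoL–ACSA | n=60 | n=100 | n=200 |
|---|---|---|---|
| 0.50 (stronger) | 1.23 vs 0.49 | 1.67 vs 0.60 | 2.32 vs 0.97 |
| 0.35 (equal) | 1.26 vs 1.03 | 1.69 vs 1.41 | 2.31 vs 2.02 |
| 0.25 (weaker) | 1.24 vs 1.19 | 1.67 vs 1.63 | 2.35 vs 2.35 |

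At n = 100 the HRQoL scale itself enters in 95%, 32% and 5% of runs. Even with HRQoL barred, fewer than three factors are kept, because the factors also overlap with each other.

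**4. One factor against one HRQoL scale** (4,000 replicates, n = 100), with correlations as (a, h, o) and the share of runs that keep the factor, barred vs eligible:

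- (0.35, 0.50, 0.60): 91% vs 10%
- (0.40, 0.40, 0.60): 97% vs 63%
- (0.50, 0.35, 0.60): 99.9% vs 98%
- (0.30, 0.60, 0.70), chosen as extreme: 80% vs 38%, always with reversed sign. The reversal follows from a − h·o = 0.30 − 0.42 = −0.12.

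**5. Would the collinearity check catch it?** For a single pair, VIF = 1/(1 − o²), which is 1.33 at o = 0.50 and 1.96 at o = 0.70. With 3 to 8 HRQoL scales (assumed correlated 0.5 to 0.8 with each other), the factor's VIF runs from 1.4 to 7.8. Whether it is flagged depends on the number of scales and on the missing cut-off.

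**The case against.** **The context separates HRQoL.** It has its own secondary objective, and an exploratory sentence that would be largely redundant if HRQoL were already in the screen. This is a fair reading of intent, and it stands as such. A reader might go further and infer that the plan intends HRQoL in the primary model; the documents do not support that. But the sentence follows the p < 0.05 rule without exempting HRQoL from it, and the word additional also fits HRQoL being tested in both places.

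**Some HRQoL scales may be biopsychosocial factors.** The plan does not define that term, and it says "the EORTC QLQ-C30 is a multidomain HRQoL instrument validated in chronic illness populations focusing on symptom and functioning scales". A sponsor could reasonably count some of these scales in. That stands, and the fix allows for it.

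**The lists are illustrative.** A reader might infer that sex, hospital setting and GDS-4 are barred from the analysis. The documents do not show this. Stage 1 in turn does not name marital status, living situation, (grand)children or hospital admissions, so the lists differ in both directions. Sex could be read into the sociodemographic heading, and the geriatric assessment entry is introduced as a list of inclusions, which softens the GDS-4 gap. These are mismatches to reconcile, not proven omissions.

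**Sensitivity analyses cover it.** Alternative model orders, bootstrapping and VIF monitoring give partial cover. They may reveal displacement but do not say which model answers the primary objective.

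**HRQoL in Stage 4 may be intended.** The clustering objective is about QoL profiles, so HRQoL inputs there are not in themselves a fault. The plan should say which is meant.

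**The simulations are not evidence about this study.** Correct. Every input is assumed, and no collinearity exclusion was applied.

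**Conclusion.** The point holds as a mismatch between a stated rule and the objective it serves. As written, Stages 2 and 3 make HRQoL scales eligible for a primary model whose objective names four other domains, and no sentence takes them out. The text does not establish that the sponsor means to include them, so confidence is medium. The doubt is about intent, not about the wording.

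The effect in this study cannot be sized. Under the assumptions shown, the loss of target factors is large when HRQoL correlates with ACSA more strongly than they do. In the three-factor runs it is modest at equal strength and close to nil when HRQoL is weaker. A single factor that overlaps closely with HRQoL can lose more at equal strength (97% to 63%). A reader might infer that frailty or activity effects will be lost or reversed in sign. The documents give no basis for that, and the sign reversal comes from one deliberately extreme configuration.

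This should be fixed before analysis. It rests on the text and not on the simulated figures.

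**What to change.** 1. In Stage 2, replace the reference to secondary outcomes with a named list for the four domains: age, sex, marital status, living situation, (grand)children, hospital setting, dialysis vintage, hospital admissions; STRATIFY, Mini-Cog, GDS-4, NRS-2002, pain VAS, vision, hearing, continence; GFI; BIA. Add sex, hospital setting and GDS-4 to the protocol's measure list to match.
2. Fit the Stage 3 primary model on that list. Analyse EQ-5D-3L, QLQ-C30 and QLQ-MY20 under the secondary objective, and label any HRQoL-added model as secondary.
3. If the sponsor regards some QLQ symptom or functioning scales as biopsychosocial factors, name those scales in advance and align the primary objective.
4. State whether HRQoL scales are Stage 4 inputs.
5. Clerical: call ACSA the dependent variable throughout. Stage 2 calls it independent, while Stage 3 models it as the outcome and Stage 4 calls it dependent.

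The cost is wording only, with no new data. The primary model's R² will probably be lower without the HRQoL scales. Overlap among the remaining candidates is not removed: GFI is itself multidimensional and stays beside the geriatric assessment items.

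### Stage 3 puts record-based factors and measures taken alongside ACSA into one forward-selected pool and calls the survivors independent predictors; pre-specify two blocks and use associational wording

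*Combined protocol and SAP*

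**What the plan says.** The protocol, Study design, gives "Model: Cross-Sectional". The Primary Objective is associational: "To identify key factors associated with overall QoL, as measured by the Amnestic Comparative Self-Assessment (ACSA"), and it covers "a range of sociodemographic, dialysis-specific, biopsychosocial, and activity-related factors, in older adults receiving ICHD". Other wording is stronger. The title speaks of predictors, the Overview closes with "identifying its key determinants among older ICHD patients", and SAP Stage 3 says "A stepwise multiple linear regression analysis is performed to identify independent predictors of overall QoL (ACSA score").

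On timing, the protocol says "Recruitment and data collection occurs during one to three consecutive dialysis sessions" and "The assessment session lasts approximately 45 minutes and includes validated instruments across several domains". ACSA, GFI, BIA and the geriatric assessment are thus gathered at essentially the same time. Age, marital and living situation, (grand)children, vintage and admissions come from medical records.

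SAP Stage 2 tests each secondary outcome against ACSA and passes those with p below 0.05 to the multivariable stage. Stage 3 enters them by forward selection and reports coefficients at each step. Under Sensitivity Analyses, "The robustness of regression findings is checked using alternative model orders and bootstrapping methods". Neither document sets blocks, a temporal order of entry, or a caution about direction.

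**The concern.** The pool holds two kinds of variable. Record-based factors such as age or vintage mostly describe circumstances that existed before the ACSA rating. GFI, BIA, pain and the other geriatric items are measured with it. The second kind may lie on the path from the first to quality of life: longer vintage may go with more frailty, and frailty with lower ACSA. Some of the second kind may also follow from low quality of life, for instance giving up advanced activities.

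Forward selection takes the strongest correlate first. Once a mediator is in the model, an upstream factor competes only on what is left of its association. The primary objective asks about four domains, two of which (sociodemographic and dialysis-specific) consist mainly of upstream factors. If the final model is read as the answer, those domains may look unimportant when they are associated with ACSA. The variables that remain carry a label that a single measurement occasion cannot justify.

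**Working it through.** **No plan figure to reproduce.** The documents give no sample size, effect size, number of candidates or entry criterion for forward selection. Every input below is an assumption except the two-sided 0.05 level and the Spearman screen, which are in the SAP (General and Stage 2). Entry to the model is assumed at p < 0.05.

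**Set-up.** All variables have unit variance, and effects are given as absolute sizes.
- U is an upstream factor and M a concurrent measure, with M = a·U + error.
- Y is ACSA, with Y = b·M + d·U + error.
- The total association of U with Y is a·b + d. The coefficient of U once M is in the model is d.
- With a = 0.4 and b = 0.5, the total is 0.4 × 0.5 + d = 0.20 + d.
- In some runs S, a pure consequence of Y (correlation 0.4 to 0.6), is added to the pool.

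Each simulated study applies the Spearman screen at 0.05 and then forward selection.

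| Direct effect d | Total | Other candidates | N | U passes screen | U retained |
|---|---|---|---|---|---|
| 0 | 0.20 | M | 100 / 150 / 250 | 47 / 65 / 86% | 3 / 2 / 3% |
| 0 | 0.20 or 0.30 | M and S | 80 to 300 | 38–100% | 2–6% |
| 0.1 | 0.30 | M | 100 / 150 / 250 | 82 / 95 / 99.6% | 18 / 28 / 42% |
| 0.1 | 0.30 | M and S | 120 / 200 | 90 / 98% | 19 / 27% |
| 0.2 | 0.40 | M and S | 120 / 200 | 98.5 / 100% | 58 / 84% |
| 0.3 | 0.50 | M and S | 120 / 200 | 100 / 100% | 93 / 99.7% |

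(In the second row, a total of 0.30 uses a = 0.30 / 0.5 = 0.6.)

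**Reading.** With d = 0 the partial coefficient of U is zero, so 2–6% is roughly the chance entry rate. At d = 0.1 the factor still has a total association of 0.30 and is usually left out. At d = 0.2 or more it is usually kept.

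**Concurrent correlate.** S, which does not cause Y at all, is retained in 88–100% of the full-mediation runs and in at least 99.5% of the partial-mediation runs.

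**U modelled without M or S.** With full mediation, U is significant in 42–46% (N = 80) to 94–96% (N = 300) of runs at a total of 0.2. At a total of 0.3 the figures are 76–79% to 100%. These runs have one upstream factor, so they do not show what mutual adjustment among several would do.

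**Order of entry.** The least-squares coefficients of a final model containing both U and M are the same whatever the order of entry. An order matters only through the intermediate steps that are reported.

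**The case against.** Five points deserve weight.

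1. *Omission can be the right answer.* Under full mediation the partial coefficient is zero, and a list of independent predictors should not contain the factor. This stands: the 2–6% is not an error rate. It shows that the question the model answers differs from whether these domains are associated with quality of life.

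2. *Stage 2 already answers the associational objective.* Largely true. The sociodemographic and dialysis variables are tested there one by one. A reader might infer that the plan discards upstream factors as non-predictors. The documents do not support that: they never use such a label, and they do not name Stage 3 as the primary model. What Stage 2 lacks is any adjustment among these factors.

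3. *Alternative orders with step-by-step coefficients could show the same thing.* They could if one order put the record-based factors first. No such order is specified, and the item is only a robustness check. Bootstrapping and variance inflation factors address stability and collinearity, not position in time.

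4. *A first block is not free of the problem.* If vintage acts through admissions with the same assumed 0.4 and 0.5, its unadjusted association is 0.4 × 0.5 = 0.20 in size, but its coefficient beside admissions is zero. This stands, so block coefficients must not be called total associations.

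5. *The split is not clean.* Admissions have no stated time window, living situation may itself follow from frailty, collection may span three sessions, and the Mini-Cog is a test and not a self-report. All true. The first block is defined by source and type of variable, not by proven precedence.

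**Conclusion.** The point holds as a risk, not a certainty. One undifferentiated, forward-selected pool in a cross-sectional study cannot guarantee an adjusted answer for the sociodemographic and dialysis-specific domains, and it cannot support the word predictors for measures taken alongside ACSA. How often an upstream factor is lost depends on how much of its association is mediated, which nobody knows here. Retention ranged from 2–6% with no direct effect to 99.7% with a direct effect of 0.3, all under assumed effects and sample sizes.

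Two stronger readings go too far. The documents do not show that upstream factors will be lost. Nor do they show that any particular concurrent measure is a consequence of low quality of life; they show only that the design cannot tell. Since Stage 2 tests the unadjusted associations and the primary objective is already worded as association, this is a cheap improvement and not a flaw that invalidates the plan.

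**What to change.** In SAP Stage 3, replace the single pool by two pre-specified blocks.

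- **Block 1:** age, sex, marital and living situation, (grand)children, vintage, hospital admissions and hospital setting. Enter them together, without univariate screening or forward selection. Report the block on its own, beside the unadjusted Stage 2 results, as associations mutually adjusted within the block and not adjusted for concurrent measures.
- **Block 2:** add GFI, BIA and the geriatric assessment items. Report the change in R² and describe these as concurrent correlates. Keep the HRQoL scores in the separate exploratory analysis; the SAP does not say at present whether they may also enter Stage 3.
- **Conclusions:** base statements on sociodemographic and dialysis-specific factors on Block 1 together with Stage 2, never on absence from the final model.
- **Wording:** in the title, Overview and Stage 3, replace predictors and determinants by the associational wording of the primary objective.

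No new data are needed. The cost is a short SAP edit, one extra regression table and a more modest claim.
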